8.3.1.5 Patient Withdrawal

Patients may withdraw from the study at any time at their own request. They may also be withdrawn at any time at the discretion of the regional study site Investigator or Sponsor if the patient's baseline MRI scan is deemed unreadable or for administrative reasons.

Patients who inform their regional study site Investigator of their intent to prematurely withdraw from the study will be asked to have a final MRI scan prior to withdrawal (unless the most recent MRI was done within three months prior to the withdrawal from the study). The regional study site Investigator will record the reason for withdrawal on the End of Study form.

Sites may not enrol additional patients to replace those who withdraw early from the study.

The study may retain and continue to use any data collected before withdrawal of consent in accordance with the original patient consent form.

8.3.1.6 Discontinuation of Lomitapide

Lomitapide may be discontinued at the request of the patient and his/her treating physician at any time during the study. If the patient discontinues lomitapide treatment, then he/she will be encouraged to have an MRI performed if the most recent MRI was more than three months prior to discontinuation of lomitapide, and to have MRI scans at approximately one and two years after discontinuing lomitapide. The Study SCC will remind the regional study site two months prior to the expected MRI dates so that the patient can be scheduled for the imaging.

8.3.2 MRI Imaging Facility Charter

A Charter will be developed by the central Imaging Core Laboratory to provide details on the imaging processes at the regional study site and at the central Imaging Core Laboratory. The guidelines set forth in the MRI Imaging Facility Charter include the following:

- MRI protocol which will describe the requirement specifications for imaging
- Image acquisition at the various sites including site qualification, acquisition methodology as well as methods of transfer of imaging data to the central Imaging Core Laboratory
- The image interpretation and analysis at the central Imaging Core Laboratory
- The central Imaging Core Laboratory systems validation procedures and documentation

8.3.3 Steering Committee

A Steering Committee will be established prior to initiation of the sub-study and will include a subset of the members of the LOWER Steering Committee such as clinicians and scientists with expertise in HoFH, cardiology, and biostatistics. The Steering Committee will also include a representative from the central Imaging Core Laboratory. The Steering Committee will be responsible for reviewing the sub-study data over time and making recommendations to Aegerion regarding the study conduct, as well as assist in study execution and interpretation and in publication planning.

8.4 Study Size

Based on published information from a randomized, placebo-controlled study on change in carotid vessel parameters as assessed by MRI (Fayad, et.al, 2011), the standard deviation of percent change from baseline to 24 months in carotid vessel wall area was estimated to be 22%. Detection of a 10% change from baseline to 24 months in carotid vessel wall area, at a two-sided α -level of 0.05 with 80% power, requires 40 evaluable patients. In order to obtain 40 evaluable patients at the two-year primary endpoint, at least 57 patients with a baseline readable MRI will be enrolled. The 57 patients to be enrolled accounts for a dropout rate of 15% over the two-year period and a 15% unreadable/unusable MRI rate.

After 20 evaluable patients have two-year MRI evaluations, a sample size re-estimation will be performed only if the conditional power of the Z-test statistic falls within the promising zone as defined by Mehta and Pocock (Mehta et. al., 2011). Further information regarding this analysis (including maximum allowable sample size) is described in Section 8.5.5. If the conditional power does not fall within the promising zone, no sample size re-estimation will be performed and the study will continue as planned (Mehta, et.al, 2011).

Should patient enrolment be much lower than anticipated, Aegerion Pharmaceuticals will propose additional measures to increase patient enrolment including opening the sub-study to other countries or regions if necessary.

8.5 Statistical Methods

A formal statistical analysis plan (SAP) will provide complete details of all statistical analyses and data presentation.

8.5.1 Efficacy Endpoints

The primary objective of the study is to assess the change in carotid atheroma as reflected by carotid vessel wall area on MRI scanning following two years of treatment with lomitapide. The endpoint used to address this objective will be the percent change in carotid vessel wall area from baseline to two years on lomitapide therapy, where percent change is calculated as $100 * \{WA(24) - WA(0)\} / WA(0)$. WA(x) denotes wall area at either baseline (x=0) or 24 months (x=24). The mean area obtained from the left and right carotid arteries will be used in the primary analysis; additional analyses will consist of individual results from the left and right arteries separately. Refer to Section 8.5.2 for the derivation of wall area measurements.

The secondary objectives of the study are:

- To assess the changes in atheroma burden as reflected by changes in average aortic vessel wall area, average aortic and carotid vessel lumen area, total vessel area, wall thickness, normalized wall index and standard deviation of wall thickness on MRI following two years of lomitapide treatment compared to baseline.

- To assess the changes in atheroma burden as reflected by changes in average aortic and carotid vessel wall area, lumen area, total vessel area, wall thickness, normalized wall index and standard deviation of wall thickness following one year and five years of lomitapide treatment compared to baseline.
- To assess changes in LDL-C and other lipoproteins at one, two and five years of lomitapide treatment compared to baseline and the correlation of these laboratory evaluations with the change from baseline in MRI parameters of carotid and aortic atheroma.

8.5.2 Efficacy Measurements

Carotid and aortic plaque burden will be measured as follows: The fat-suppressed black-blood fast spin echo proton density or T2 weighted images will be analyzed with a semi-automated algorithm to segment the inner lumen boundary and outer vessel wall area at the adventitial layer. Subtraction of the lumen area from the outer vessel wall area provides the vessel wall area. Mean carotid vessel wall area is obtained from the analysis of the serial images that cover the bilateral common carotid arteries. Mean aortic wall areas are obtained in three segments: the ascending aorta, the descending thoracic aorta and descending abdominal aorta. Average vessel wall area (mm^2) = sum of wall area for each slice/total number of slices will be computed. The images will be matched for locations across visits using anatomical landmarks.

Total carotid plaque burden derived from MRI is reported from the individual carotid arteries as well as the average vessel wall area of both left and right carotid arteries.

Exploratory endpoints will include the lumen area, total vessel area, standard deviation of wall thickness and the normalized wall index. Mean wall thickness measurements are obtained using the centerline method and are obtained for each slice separately and averaged. Measurements are obtained from both carotids and the aortic segments described previously for wall area measurements. The normalized wall index (NWI) is the ratio of the vessel wall area divided by the total vessel area.

Carotid Plaque Composition - The axial multi-contrast proton density (PD), T1 and T2 weighted) black-blood images obtained in the carotid will be analyzed with a semi-automated algorithm to determine inner and outer vessel wall boundaries as well as major plaque compositional features determined from the contrast patterns across each of the

three images acquired at the same location. The major features include the necrotic lipid area, fibrous cap thickness and calcium area. These are quantified as either present or absent by subjective analysis.

8.5.3 Analysis Populations

8.5.3.1 Modified Intent-to-Treat (MITT) Population

The modified intent-to-treat (MITT) population consists of all enrolled patients with a readable baseline MRI. The terminology “readable MRI” is an image that can be read and interpreted by the central Imaging Core Laboratory for the study. The primary analysis of efficacy will use this population. Imputation methods as outlined in [Section 8.5.6](#) will be used for missing data for the 2-year MRI evaluation for the MITT patient population.

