8.3.1.1 Regional Study Site Enrolment Visit

At the LOWER enrolment visit, after the patient has provided written consent to participate in LOWER, the LOWER enrolling physician (or designee) will provide an overview of this vascular imaging study to each patient. The LOWER enrolling physician will notify the SCC of interested patients. The SCC will then notify the regional study

site. The regional study site will contact the patient to assess eligibility and obtain informed consent. For patients who are not located near the regional site, verbal informed consent will be obtained first by phone with written informed consent obtained at the baseline visit, prior to any procedures being performed. Enrolled patients will have a baseline MRI scan at the regional study site prior to initiating lomitapide therapy or within three months after initiating lomitapide therapy.

The following will be collected at the enrolment visit:

- Date of written informed consent
- Confirmation of eligibility criteria
- Laboratory tests (lipoprotein, inflammatory and cardiovascular biomarkers)
 - Lipoprotein biomarkers
 - Total cholesterol (TC)
 - High density lipoprotein (HDL-C)
 - Low density lipoprotein (LDL-C)
 - Triglycerides (TG)
 - Apolipoprotein B (apo B)
 - Apolipoprotein A-I (apo AI)
 - Lipoprotein (a) (Lp(a))
 - Apolipoprotein C-III (Apo C-III)
 - LDL sub-fractions using nuclear magnetic resonance (NMR) technology
 - Inflammatory and cardiovascular biomarkers
 - High sensitivity C reactive protein (hs-CRP)
 - Serum amyloid A (SAA)
 - Soluble Inter-cellular Adhesion Molecule-1 (sICAM-1)
 - Interleukin 6 (IL-6)
 - Lipoprotein Associated Phospholipase 2 (LpPLA2)
 - Soluble Vascular Cell Adhesion Protein 1 (sVCAM-1)
 - Soluble E-selectin (sE-selectin)

- Fasting glucose and insulin and calculate HOMA (Homeostasis Model Assessment)
- Baseline MRI

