8.3.1.2 Baseline MRI Scan

In order to be eligible for this study, a patient must have his/her baseline MRI scan within three months after initiating therapy with lomitapide. The baseline MRI should ideally be scheduled as soon as possible after enrolment and prior to initiation of lomitapide therapy.

Patients must have a baseline MRI scan that is deemed evaluable with an acceptable image quality of carotid arteries (both left and right carotid arteries) and aorta as determined by the central Imaging Core Laboratory in order to proceed to the follow up visits. All MRI scans must be immediately sent to the central Imaging Core Laboratory for qualitative image analysis. The central Imaging Core Laboratory will provide a rapid turnaround (within one week) of the image quality evaluation. The image quality evaluation will be sent to the regional study site as well as to the SCC so that, in the event that a repeat MRI is required, the site can contact the patient to return for additional scans.

Each regional study site will provide data to the central Imaging Core Laboratory following the guidelines set forth in the MRI Imaging Facility Charter ([Section 8.3.2](#)). The central Imaging Core Laboratory will notify the regional study site and the SCC that the MRI is acceptable, or if a repeat MRI is required. The SCC will request that the regional study site Investigator or his/her designee either complete the notification form if the testing was completed or contact the patient and schedule a repeat MRI. An MRI image deemed acceptable by the central Imaging Core Laboratory must be confirmed within three months of the patient starting lomitapide treatment. If delays result in the imaging being done outside of the three month window since starting lomitapide treatment, the patient will not be eligible to continue in the study.

The central Imaging Core Laboratory will transfer analysed results to SCC in a pre-specified format and time-frame as specified in the DMP.

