8.5.3.3 Safety Population

The safety population consists of all enrolled patients who have received at least one dose of lomitapide.

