8.5.6 Missing Observations

It is unlikely that patients would withdraw from the trial due to the nature of this disease; however, this possibility must be addressed. Patients will be strongly encouraged to continue in the study, and if withdrawal is necessary, they will be encouraged to obtain an MRI prior to discontinuation. Missing data for the primary endpoint of carotid vessel wall area (CVWA) obtained at 2 years, due to an unavailable or unreadable MRI at year 2, is also possible. To help minimize unreadable MRI results, patients with follow up MRIs that are considered unreadable will be requested to have a repeat MRI performed within the 2 month window. A thorough evaluation will be performed prior to data analysis, to determine the causes for any unavailable MRI results at 2 years. In particular, the possibility that missing MRI results are related to response to lomitapide therapy will be evaluated, in order to determine if MRI data are missing at random or not. For patients with no available readable MRI at 2 years, the following imputation method will be used.

For patients that could reasonably be considered to have data missing at random, such as resulting from inability to travel to the MRI center, a standard multiple imputation technique, using the predictive characteristics of complete cases (patients with 2-year

MRI data), will be used to account for these missing data in analysis. These predictive characteristics will include, for example, age, sex, lipid measurements over time, MRI results obtained prior to 2 years, etc. For patients whose data cannot reasonably be determined to be missing at random, an approach to multiple imputation will be used wherein the value to be used in each iteration of the method will be a random selection of a data point from the set of values from all patients with an available percent reduction from baseline in carotid vessel wall area at the two-year evaluation who have shown an increase in CVWA (worsened). This approach would therefore apply a conservative value that also would not artificially decrease variability.

Similar methods will be used for the assessment of, and imputation for, secondary endpoints as appropriate. Sensitivity analyses of the primary endpoint will be performed to assess the effect of missing data on the two-year endpoint, including repeated measure mixed model procedures and complete-case analysis.

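### The primary MITT population has no lomitapide-dose condition, so the few patients who are scanned before treatment and never start would count towards the drug's effect.

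*Protocol*

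**What the plan says.** Protocol 8.5.3.1 states that the MITT "population consists of all enrolled patients with a readable baseline MRI" and adds: "The primary analysis of efficacy will use this population". Those are the only two conditions, and missing two-year scans in this set are imputed under 8.5.6.

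Protocol 8.5.3.3 sets a different condition for safety: "The safety population consists of all enrolled patients who have received at least one dose of lomitapide".

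Protocol 8.5.1 defines the primary endpoint as "percent change in carotid vessel wall area from baseline to two years on lomitapide therapy". Section 8.5.4.2 tests it with a one-sample t-test in the MITT population, and 8.9.1 reads the within-patient result as an estimate of lomitapide's effect.

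On the timing of the baseline scan, 8.3.1.1 says: "Enrolled patients will have a baseline MRI scan at the regional study site prior to initiating lomitapide therapy or within three months" of the start of therapy. Section 8.3.1.2 states a preference: "The baseline MRI should ideally be scheduled as soon as possible after enrolment and prior to initiation of lomitapide therapy".

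On entry, 8.2.1 describes the target population by the decision to prescribe. The inclusion criteria (3.6.1 and 8.2.1.1) are tighter: the patient must be starting lomitapide at enrolment or have started within the previous three months.

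For missing two-year scans, 8.5.6 uses "a standard multiple imputation technique, using the predictive characteristics of complete cases" when the data can be considered missing at random. Otherwise it draws values at random from patients whose wall area increased.

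**The concern.** The population and the endpoint do not match for one kind of patient. Someone enrolled as starting lomitapide, scanned before the first dose and then never treated meets both MITT conditions, but cannot have a change on lomitapide therapy.

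The preferred order of events, scan first and drug second, is what opens this route. The drug is commercial and prescribed in usual care, so the study does not control whether the first dose is taken. The separate dose condition for safety shows that the protocol itself distinguishes enrolled from dosed.

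The study has no control arm. Keeping undosed patients therefore protects no randomised comparison, which is the usual reason for keeping them. At stake is how cleanly the single-arm mean can be read as the effect of the drug.

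**Working it through.** **1. Can a never-dosed patient be in the MITT set?**
- Entry (8.2.1.1): starting at enrolment is enough, and that can be met before any tablet is taken.
- Baseline scan (8.3.1.1, 8.3.1.2): allowed, and preferred, before the first dose.
- MITT (8.5.3.1): enrolled with a readable baseline scan. Both are met.
- Removal: 8.3.1.5 names patient request, an unreadable baseline scan and administrative reasons. Section 8.3.1.6 covers stopping the drug, not failure to start it. No section expressly removes this patient.

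So the answer is yes, in a narrow case.

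**2. What happens to that patient's data?**
- Two-year scan available: an untreated change enters the test. Section 8.5.4.2 itself considers reduction unlikely without lipid-lowering therapy, so the expected result is dilution.
- Scan missing, judged at random: the value is imputed from complete cases, nearly all treated, which gives an untreated patient a treated response.
- Scan missing, not judged at random: the value is drawn from patients who worsened.

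The bias therefore has no single direction.

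**3. The plan's own figure.** Inputs from 8.4: 10% reduction, SD 22%, two-sided 5% level, 80% power, 40 evaluable, at least 57 enrolled. For a one-sample t-test the noncentrality at n = 40 is 10 / (22/√40) = 2.875, and power is 0.8005. The 40 is reproduced. Inflating for two losses of 15%, 40/0.70 = 57.1 matches the stated 57 (multiplying the two rates gives 40/0.85² = 55.4).

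**4. Illustration: one never-starter in 40.** The share q = 1/40 = 0.025 is an assumption, because the documents give no rate. Let c be the true percent reduction in a never-starter.

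Mean = (1 − q)·10 + q·c; SD = √(22² + q(1 − q)(10 − c)²).

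| c | Mean | SD | Noncentrality | Power, n = 40 |
|---|---|---|---|---|
| no never-starter | 10 | 22 | 2.875 | 0.80 |
| 0 (no change) | 0.975 × 10 = 9.75 | √(484 + 0.024375 × 100) = 22.06 | 2.796 | 0.78 |
| −5 (assumed 5% progression) | 9.75 − 0.125 = 9.625 | √(484 + 0.024375 × 225) = 22.12 | 2.751 | 0.77 |

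Leaving that patient out instead gives n = 39 and power 0.79, so the loss due to keeping the patient is smaller still.

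**5. Limit of the illustration.** It treats 40 observed patients as the analysis set. The MITT set is at least 57 with imputation. If all 57 were observed, an upper bound, power would be 0.92 with no never-starters and about 0.91 with one (q = 1/57) for either value of c. The effect of the imputation route is not quantified here.

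**The case against.** The strongest reply is that such patients should hardly exist. The inclusion criteria require that treatment is starting or has started, 8.1 speaks of patients being treated, and one sentence of 8.3.1.2 ties eligibility to a scan within three months after the start of therapy. Read literally, that sentence would exclude a never-starter. This stands as to frequency: very few are to be expected. It does not close the gap, because 8.3.1.1 and the next sentence of 8.3.1.2 accept a scan before treatment and 8.5.3.1 is unaffected.

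A reader might infer a material loss of power. With the same formulas, a 10% never-start share with no change would give 0.705 at n = 40. The documents support no such share, the entry criteria argue against it, and n = 40 is not the MITT set: with 57 observed the same share gives 0.85.

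A reader might also infer that imputing never-starters makes the result look falsely precise. That is not shown. Multiple imputation carries the between-imputation variance into the standard error, so an imputed patient does not count as a full observation.

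It is also fair to say that a one-dose rule does not fully match population to endpoint, since a patient who stops after one dose does not have two years on therapy either. That stands. The per-protocol population (8.5.3.2) and the complete-case analysis (8.5.6) give some cover, but neither is the primary analysis.

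Finally, the SAP, which was not available for this check, might add a dose condition. Section 8.5.3.2 leaves further criteria to it for the per-protocol set. Section 8.5.3.1 does not do so for MITT, so such a condition would alter the protocol's definition.

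**Conclusion.** The point holds as a gap in a definition. The primary efficacy set lacks the dose condition that the endpoint implies and that the safety set already has, and no section removes a patient who is scanned and never starts.

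Its size is small. The documents give no never-start rate, and the 40 and 57 stand unchanged. One never-starter in 40 would move power from 0.80 to about 0.78 with no change in wall area, or 0.77 with 5% progression. Both the count and the progression are assumptions. The direction of bias depends on whether the patient is scanned at two years and, if not, on how the missing value is classified. Neither a large power loss nor an overstated precision follows from the text.

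The gap is still worth closing, because the correction is cheap and the single-arm mean is read as the effect of lomitapide.

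**What to change.** In 8.5.3.1, add the condition that the patient received at least one dose of lomitapide, and carry the same wording into the SAP. Identify dosed patients from the LOWER exposure data, which 8.3.1 already transfers to the study database. Count never-dosed patients in the disposition summary (8.5.4.1). Describe any follow-up scans they have separately, outside the primary test and outside the imputation model in 8.5.6.

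The cost is one clause and no new data. The MITT count may fall by a very few patients. The clause settles only the never-dosed; how the primary analysis treats patients who discontinue after starting is a separate question that it does not answer.

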8.5.3.2 Per-protocol (PP) Population

The per-protocol (PP) population consists of all enrolled patients who adhere to the protocol-specified study requirements. These patients will include those for whom a baseline MRI and a two-year MRI exist and are readable. Patients in the PP population must also satisfy additional explicit criteria for eligibility that will be included in the SAP prior to the start of this study. The PP population may generally be considered a complete-case population.

